5.5.2.2.11. Analysis Related to Treatment Satisfaction Questionnaire for Medications

- The TSQM-9 domains will be summarized over time by treatment groups.

5.6. Safety Analyses

All safety analyses will be performed using safety analysis set based on actual intervention received. No formal statistical comparison is planned.

For all continuous safety variables, descriptive statistics by intervention group will include the N, mean, standard deviation, median, minimum, and maximum. Categorical variables will be summarized by intervention group using frequency counts and percentages.

Depending on the study, the cumulative safety data will be analyzed through different study and study periods as shown below. Unless otherwise specified, tabular summaries of safety events are also presented as following:

Study 77242113PSO2001

The safety data through the end of the main study 77242113PSO2001 will be included and safety analysis set (Section 4.1) will be used. For participants who entered 7242113PSO2002 study at the time of Week 16 visit (without a gap period), safety data through Week 16 are included. For participants who completed the participation of the 77242112PSO2001 study but either had a delay in joining or didn't participate 77242113PSO2002 study, safety data through end of the study are included. Safety data through the end of the 77242113PSO2001 study will be summarized by following intervention group:

- Placebo
- JNJ-77242113 25 mg QD
- JNJ-77242113 50 mg AD
- JNJ-77242113 25 mg BID
- JNJ-77242113 100 mg QD
- JNJ-77242113 100 mg BID
- Combined JNJ-77242113 groups

Study 77242113PSO2002

(a) Safety data from Week 16 (Week 0 of 77242113PSO2002 study) through Week 56 (Week 40 of 77242113PSO2002 study) for participants enter the 77242113PSO2002 will be included and LTE safety analysis set (Section 4.2) will be used. Safety data from Week 16 through Week 56 will be summarized by following intervention group:

- Placebo → JNJ-77242113 100 mg QD
- JNJ-77242113 25 mg QD
- JNJ-77242113 50 mg QD
- JNJ-77242113 25 mg BID
- JNJ-77242113 100 mg QD
- JNJ-77242113 100 mg BID
- Combined JNJ-77242113 groups

(b) Safety data through Week 56 (Week 40 of 77242113PSO2002 study) with the combined data of 77242113PSO2001 and 77242113PSO2002 studies will be included and safety analysis set (Section 4.2) will be used. Safety data through Week 56 will be summarized by following intervention groups.

- Placebo
- Placebo → JNJ-77242113 100 mg QD
- JNJ-77242113 25 mg QD
- JNJ-77242113 50 mg QD
- JNJ-77242113 25 mg BID
- JNJ-77242113 100 mg QD
- JNJ-77242113 100 mg BID
- Combined JNJ-77242113 groups

5.6.1. Extent of Exposure

The extent of exposure will be summarized for randomized participants that received at least one study agent administration. Distribution of participants through Week 16 and through Week 52 by study agent lot will be analyzed for 77242113PSO2001 and 77242113PSO2002 respectively. In addition, the number (%) of participants receiving the study drug during double blind treatment phase will be summarized by treatment group.

The total duration of exposure to study medication (days), including days off medication, will be calculated as:

Total duration of exposure = last day of study medication - first day of study medication + 1.

5.6.2. Adverse Events

The verbatim terms used in the CRF by investigators to identify adverse events will be coded using the Medical Dictionary for Regulatory Activities (MedDRA). Any AE occurring at or after the initial administration of study intervention is considered to be treatment emergent. If the event occurs on the day of the initial administration of study intervention, and either event time or time of administration are missing, then the event will be assumed to be treatment emergent. If the event date is recorded as partial or completely missing, then the event will be considered to be treatment emergent unless it is known to be prior to the first administration of study intervention based on partial onset date or resolution date. All reported treatment-emergent adverse events will be included in the analysis. For each adverse event, the number and percentage of participants who experience at least 1 occurrence of the given event will be summarized by intervention group.

Summary tables will be provided for treatment-emergent adverse events:

- AEs
- Serious AEs (SAEs)
- AEs leading to discontinuation of study intervention
- AEs of severe intensity
- AEs related to study intervention

In addition to the summary tables, listings will be provided for participants who:

- Had SAEs
- Had AEs leading to discontinuation of study intervention
- Had AEs of severe intensity
- Had AE for psoriasis

- Had suicidal ideation or suicidal behavior
- Had anaphylactic or serum sickness reactions

A listing of participants who died will be provided.

Since safety should be assessed relative to follow-up, most AE summary tables will include average weeks of follow-up for each intervention group.

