- The proportion of participants who achieve PSSD signs score=0 at Week 16 will be compared between each of the JNJ-77242113 groups and the placebo group among participants with a baseline PSSD signs score ≥ 1 .
- The proportion of participants with DLQI=0 or 1 at Week 16 will be compared between each of the JNJ-77242113 groups and the placebo group respectively among participants with a baseline DLQI score > 1 .
- The proportion of participants who achieve 5-point improvement or higher in each PROMIS-29 domain from baseline to Week 16 will be compared between each of the JNJ-77242113 groups and the placebo group.
- The change from baseline in BSA at Week 16 will be compared between each of the JNJ-77242113 groups and the placebo group.

- The change from baseline in PROMIS-29 domain scores at Week 16 will be compared between each of the JNJ-77242113 groups and the placebo group.

Safety Analyses

Safety data, including but not limited to, AEs, SAEs, AESIs (active TB, malignancy, potential Hy's Law cases), discontinuation of study intervention due to AEs, changes in laboratory assessments, changes in vital signs, and changes in weight will be summarized. Intervention-emergent AEs will be summarized by treatment group and Medical Dictionary for Regulatory Activities (MedDRA) system organ class and preferred terms. Details will be specified in the SAP.

Adverse Events

The verbatim terms used in the electronic case report form (eCRF) by investigators to identify AEs will be coded using the MedDRA. Intervention-emergent AEs are AEs with onset during the intervention period or that are a consequence of a preexisting condition that has worsened since baseline. All intervention-emergent AEs will be included in the analysis. For each AE, the percentage of participants who experience at least 1 occurrence of the given event will be summarized by intervention group. In addition, comparisons between intervention groups will be provided if appropriate.

The following analyses will also be used to assess the safety of participants in the study:

- The incidence and type of AEs.
- The incidence and type of SAEs.
- The incidence and type of severe AEs.
- The incidence and type of related AEs as assessed by the investigator.
- The incidence and type of AEs leading to discontinuation of study.

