8.3. Adverse Events, Serious Adverse Events, and Other Safety Reporting

Timely, accurate, and complete reporting and analysis of safety information, including AEs, SAEs, and product quality complaint (PQC), from clinical studies are crucial for the protection of participants, investigators, and the sponsor, and are mandated by regulatory agencies worldwide. The sponsor has established Standard Operating Procedures in conformity with regulatory requirements worldwide to ensure appropriate reporting of safety information; all clinical studies conducted by the sponsor or its affiliates will be conducted in accordance with those procedures.

Adverse events will be reported by the participant (or, when appropriate, by a caregiver, surrogate, or the participant’s legally acceptable representative) for the duration of the study. Collection of additional medical records may be requested by the medical monitor or the sponsor to support safety monitoring and reporting.

Further details on AEs, SAEs, and PQC can be found in Section 10.6.

8.3.1. Time Period and Frequency for Collecting Adverse Event and Serious Adverse Event Information

All Adverse Events

All AEs and special reporting situations, whether serious or non-serious, will be reported from the time a signed and dated ICF is obtained until completion of the participant's last study-related procedure, which may include contact for follow-up of safety. Any clinically relevant changes during the study must be recorded in the AE section of the eCRF.

Serious Adverse Events

All SAEs, as well as PQC, occurring during the study must be reported to the appropriate sponsor contact person by study site personnel within 24 hours of their knowledge of the event.

Serious adverse events, including those spontaneously reported to the investigator within 4 weeks after the last dose of study intervention, must be reported. The sponsor will evaluate any safety information that is spontaneously reported by an investigator beyond the time frame specified in the protocol.

Information regarding SAEs will be transmitted to the sponsor using the SAE Form, which must be completed and signed by a physician from the study site and transmitted to the sponsor within 24 hours. The initial and follow-up reports of a SAE should be transmitted electronically or by facsimile (fax). Telephone reporting should be the exception and the reporter should be asked to complete the appropriate form(s) first.

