9.4.5. Safety Analyses

Safety data, including but not limited to, AEs, SAEs, AESIs (active TB, malignancy, potential Hy's Law cases), discontinuation of study intervention due to AEs, changes in laboratory assessments, changes in vital signs, and changes in weight will be summarized. Intervention-emergent AEs will be summarized by treatment group and Medical Dictionary for Regulatory Activities (MedDRA) system organ class and preferred terms. Details will be specified in the SAP.

Adverse Events

The verbatim terms used in the eCRF by investigators to identify AEs will be coded using the MedDRA. Intervention-emergent AEs are AEs with onset during the intervention period or that are a consequence of a preexisting condition that has worsened since baseline. All intervention-emergent AEs will be included in the analysis. For each AE, the percentage of participants who experience at least 1 occurrence of the given event will be summarized by intervention group. In addition, comparisons between intervention groups will be provided if appropriate.

The following analyses will also be used to assess the safety of participants in the study:

- The incidence and type of AEs.
- The incidence and type of SAEs.
- The incidence and type of severe AEs.
- The incidence and type of related AEs as assessed by the investigator.
- The incidence and type of AEs leading to discontinuation of study.

Listings of participants with SAEs, severe AEs, AEs for psoriasis, AEs leading to discontinuation of study and anaphylactic reaction/serum sickness reactions will also be provided. All safety analyses will be based on the population of participants who received at least 1 administration of study intervention; participants will be summarized by the intervention they received.

Clinical Laboratory Tests

Laboratory data will be summarized by type of laboratory test (eg, hematology, clinical chemistry). Selected laboratory parameters will be summarized by treatment groups. Common Terminology Criteria for Adverse Events (CTCAE) and ULN will be used to identify abnormal laboratory test results, and the incidence and severity of abnormal laboratory parameters (hematology and chemistry) will be summarized by treatment group.

In addition, a listing of participants with Grade 2 or higher laboratory test results (based on the CTCAE criteria) will also be provided.

C-SSRS

Suicide-related thoughts and behaviors based on the C-SSRS will be summarized descriptively by treatment group.

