10.6.1. Adverse Event Definitions and Classifications

Adverse Event

An AE is any untoward medical occurrence in a clinical study participant administered a pharmaceutical (investigational or non-investigational) product. An AE does not necessarily have a causal relationship with the intervention. An AE can therefore be any unfavorable and unintended sign (including an abnormal finding), symptom, or disease temporally associated with the use of a medicinal (investigational or non-investigational) product, whether or not related to that medicinal (investigational or non-investigational) product. (Definition per International Council for Harmonisation [ICH]).

This includes any occurrence that is new in onset or aggravated in severity or frequency from the baseline condition, or abnormal results of diagnostic procedures, including laboratory test abnormalities.

Note: The sponsor collects AEs starting with the signing of the ICF (refer to Section [8.3.1](#), for time of last AE recording).

Serious Adverse Event

An SAE based on ICH and EU Guidelines on Pharmacovigilance for Medicinal Products for Human Use is any untoward medical occurrence that at any dose:

- Results in death
- Is life-threatening
(The participant was at risk of death at the time of the event. It does not refer to an event that hypothetically might have caused death if it were more severe.)
- Requires inpatient hospitalization or prolongation of existing hospitalization
- Results in persistent or significant disability/incapacity
- Is a congenital anomaly/birth defect
- Is a suspected transmission of any infectious agent via a medicinal product
- Is Medically Important*

*Medical and scientific judgment should be exercised in deciding whether expedited reporting is also appropriate in other situations, such as important medical events that may not be immediately life-threatening or result in death or hospitalization but may jeopardize the participant or may require intervention to prevent one of the other outcomes listed in the definition above. These should usually be considered serious.

If a serious and unexpected AE occurs for which there is evidence suggesting a causal relationship between the study intervention and the event (eg, death from anaphylaxis), the event must be

reported as a serious and unexpected suspected adverse reaction even if it is a component of the study endpoint.

Unlisted (Unexpected) Adverse Event/Reference Safety Information

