6.2. Appendix 2 Changes to Protocol-Planned Analyses

N/A

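### The SAP's treatment-emergent rule omits, without declaring it, the protocol's clause for worsened preexisting conditions, so a screening-onset AE that worsens on treatment can be missed in the AE frequency tables

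*SAP*

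**What the plan says.** Protocol 9.4.5 defines the events to be analysed by two routes: "Intervention-emergent AEs are AEs with onset during the intervention period or that are a consequence of a preexisting condition that has worsened since baseline". The synopsis repeats the definition. The protocol leaves details of the safety analysis to the SAP.

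SAP 5.6.2 uses one route: "Any AE occurring at or after the initial administration of study intervention is considered to be treatment emergent". An event on the day of first dosing with a missing time counts as emergent. An event with a partial or missing date also counts "unless it is known to be prior to the first administration of study intervention based on partial onset date or resolution date". Nothing is said about worsening.

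The same SAP section restricts its tabulations: "Summary tables will be provided for treatment-emergent adverse events". There are five tables: all AEs, serious AEs, AEs leading to discontinuation of study intervention, severe AEs and related AEs. The listings that follow are not worded as restricted in this way.

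Under Protocol 8.3.1, AEs "will be reported from the time a signed and dated ICF is obtained". Protocol 10.6.1 says of the AE definition: "This includes any occurrence that is new in onset or aggravated in severity or frequency from the baseline condition".

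The SAP's Appendix 2, headed "Changes to Protocol-Planned Analyses", contains only N/A.

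**The concern.** The SAP has dropped half of a protocol definition without saying so. This matters because screening can last up to 4 weeks and AEs are recorded throughout it. Some AE records will therefore carry an onset date before the first dose. If such an event becomes worse on treatment, the protocol's second route is what would bring it into the analysis, and the SAP does not contain it.

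The frequency and type of AEs and SAEs is a secondary endpoint in the first study of this compound in patients with psoriasis. Frequencies by arm come from the summary tables, so an event that is not classed as emergent does not contribute to that endpoint.

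**Working it through.** There is no planned figure to reproduce. The check is to apply the SAP rule to each way in which a worsening can be recorded.

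1. **A medical-history condition worsens after the first dose.** Protocol 10.6.1 makes the aggravation itself an AE. It first becomes an AE when it worsens, which is after dosing. The SAP counts it.
2. **An AE starts in screening, worsens after the first dose, and the worsening is entered as a new AE.** The new record is dated after dosing. The SAP counts it.
3. **The same event is kept as one record with its screening onset date.** Under the protocol, the worsening clause can bring it in. Under the SAP, the outcome turns on the word occurring. The only dates the SAP uses to settle unclear cases are onset and resolution, never a date of worsening, which favours reading the word as onset. On that reading the event is not emergent and is absent from all five tables. If occurring meant ongoing, every unresolved screening AE would count, including those that never changed. Neither reading reproduces the protocol's rule.
4. **An event on the dosing day has no time, or an event has a partial or missing date and is not known to precede dosing.** The SAP counts it.

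Only case 3 is exposed. Whether it arises depends on how sites record a change in severity:

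- Protocol 10.6.3 gives three severity grades but does not say what to do when the grade changes.
- Protocol 10.6.5 calls for a new SAE in one narrow setting, where an AE prolongs a hospitalization that was already planned.
- Protocol 8.2 and 8.3.1 want clinically relevant changes entered in the AE section of the eCRF, but do not say whether that means a new record or an update to the open one.

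**Size.** The documents give no rate of screening-onset AEs, no rate of worsening, and no share kept as one record. As pure assumptions, take 5% to 15% of 240 participants with a screening-onset AE and 10% to 20% of those worsening after dosing:

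- 240 × 0.05 × 0.10 = 1.2 participants
- 240 × 0.15 × 0.20 = 7.2 participants
- Over six arms: 1.2 / 6 = 0.2 to 7.2 / 6 = 1.2 per arm

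These figures must be multiplied by the share kept as one record, which could be anything from 0 to 1. The range is therefore 0 to about 7 participants in the whole study, and its upper end rests on nothing in the documents. For scale, 1 / 40 = 2.5 percentage points in one arm.

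**The case against.** The strongest defence is that the protocol's AE definition already does the work. An aggravation is an AE in its own right, so a worsening after dosing is an AE occurring after dosing, and the SAP counts it. This stands for cases 1 and 2, and it is why a reader who infers that worsened events leave every AE table would be going too far. It does not settle case 3, because no general recording rule says that a rise in severity opens a new record. The protocol also contains that same AE definition and still includes the worsening clause.

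A reader might also take the SAP to count only events with onset after the first dose. The wording does not support that: it says occurring at or after, and it includes same-day events without a time and undated events by default.

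Serious worsening would not be hidden. The listings of serious, severe, discontinuation and psoriasis AEs are not limited to emergent events. SAEs reach the sponsor within 24 hours, and SAP 5.8.1 has the data monitoring committee review them monthly. Laboratory, vital-sign and C-SSRS worsening is summarized separately, without using the AE rule. All of this stands. But listings do not supply the frequencies by arm, and a mild-to-moderate worsening appears in no listing unless it falls into one of the named categories.

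Finally, it is tempting to conclude that the tables lean towards safety. The documents do not show this as a between-arm effect, because the rule applies equally to placebo. A drug-placebo difference would shrink only if the drug itself caused the worsening.

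**Conclusion.** The point holds in a limited form. The SAP's definition departs from the protocol's, and the departure is not declared. The consequence is confined to an AE that opens between consent and first dose, worsens after dosing, and is kept as one record with its pre-dose onset date. Such an event can be left out of the five summary tables. The effect is a possible understatement of incidence in any arm. Its size is unknown and may be zero.

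This rests on two assumptions: that occurring is applied as onset in programming, and that at least some sites update an open record instead of starting a new one. The documents neither confirm nor exclude either. The departure from the protocol's definition stands whatever the answer.

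**What to change.** Restore the protocol's second route in SAP 5.6.2. Suitable wording to add: or any AE with onset before first administration that worsens in severity or becomes serious on or after first administration.

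Also state how a severity increase after the first dose is recorded and dated, for example as a new AE record dated at the worsening. Without this the added clause may not be programmable, because the documents do not show a field for the date on which severity changed.

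If the timing-only rule is intended, declare it in Appendix 2 and give the reason.

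The cost is one sentence, one derivation rule and possibly a CRF completion instruction to sites.

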5.6.3. Additional Safety Assessments (if applicable)

5.6.3.1. Clinical Laboratory Tests

Clinical laboratory tests will be displayed for the participants included in the safety analysis set.

Descriptive statistics and graphical displays will be presented for selected chemistry and hematology laboratory tests at scheduled time points.

Change from baseline through different study periods in both studies as specified in Section 5.6 will be summarized for chemistry, and hematology tests and displayed by intervention group. Box plots of laboratory measurements and change from baseline will be provided for the selected laboratory measurement.

- **Hematology** will include but are not limited to the following: Basophils, Eosinophils, Hemoglobin, Lymphocytes, Monocytes, Neutrophils, Platelets, WBC, CRP and ESR.
- **Chemistry** will include but are not limited to the following: ALT, AST, Albumin, Alkaline Phosphatase, Bicarbonate (CO₂), Corrected Calcium, Chloride, Creatinine, GGT, Glucose, Potassium, SGOT, SGPT, Sodium, Total Bilirubin, Total Protein, Urea Nitrogen.

Applicable laboratory results will be graded according to National Cancer Institute's Common Terminology Criteria for Adverse Events (NCI-CTCAE). The proportion of participants with post-baseline values by maximum toxicity grade for clinical laboratory tests will be summarized by study intervention group. Participants with toxicity grades ≥ 2 will be listed.

In addition, for selected laboratory parameters, ULN will also be used to identify abnormal laboratory test results, and the incidence and severity of abnormal laboratory parameters (hematology and chemistry) will be summarized by treatment group. Participants with maximum post-baseline elevated liver function tests through Week 16 (77242113PSO2001) and through Week 56 relative to ULN will be summarized in categories as shown below will be provided.:

- $> 1 \times$ ULN
- $\geq 3 \times$ ULN
- $\geq 5 \times$ ULN
- $\geq 10 \times$ ULN

- $\geq 20 \times \text{ULN}$

In addition, Summary of potential Hy's Law case (ALT or AST $\geq 3 \times \text{ULN}$ and total bilirubin $\geq 2 \times \text{ULN}$) through Week 16 and Week 56 respectively will also be provided.

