5.6.3.2. Vital Signs

Continuous vital sign parameters including pulse, blood pressure (systolic and diastolic) will be summarized at each assessment time point. Change from baseline by study and study periods as specified in Section 5.6 will be summarized. Descriptive statistics (mean, standard deviation, median, minimum and maximum) will be presented.

Incidence of treatment-emergent abnormal vital signs during intervention, as defined in Table 6, will be summarized for participants who had a baseline assessment and at least 1 postbaseline assessment for that vital sign.

Table 6: Clinically Important/Markedly Abnormal Vital Signs

Vital Sign	Criteria
Pulse	$>[120]$ bpm and with $>[30]$ bpm increase from baseline
	$<[50]$ bpm and with $>[20]$ bpm decrease from baseline
Systolic blood pressure	$>[180]$ mm Hg and with $>[40]$ mm Hg increase from baseline
	$<[90]$ mm Hg and with $>[30]$ mm Hg decrease from baseline
Diastolic blood pressure	$>[105]$ mm Hg and with $>[30]$ mm Hg increase from baseline
	$<[50]$ mm Hg and with $>[20]$ mm Hg decrease from baseline
Respiratory rate	$>[20]$ breaths per minute

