6.11. Appendix 11 Laboratory Toxicity Grading

The grading scale use for lab assessments is based on ‘Common Terminology Criteria for Adverse Events (CTCAE) v5.0’.

If a laboratory value falls within the grading as specified below but also within the local laboratory normal limits, the value is considered to be normal and will be reset to grade 0.

Pre-baseline measurements will use the same grading ranges as applied to baseline measurements. In case a test has two sets of ranges – one for baseline normal and one for baseline abnormal, the one for baseline normal will be applied for all measurements taken pre-baseline and on baseline.

Text in gray italic in the table is present in the grading scale, but is not applied by Janssen when grading lab data.

CTCAE Term	Grade 1	Grade 2	Grade 3	Grade 4	Janssen implementation notes
Blood and lymphatic system disorders					
Anemia	Hemoglobin (Hgb) <LLN - 10.0 g/dL; <LLN - 6.2 mmol/L; <LLN - 100 g/L	Hemoglobin (Hgb) <10.0 - 8.0 g/dL; <6.2 - 4.9 mmol/L; <100 - 80g/L	Hemoglobin (Hgb) <8.0 g/dL; <4.9 mmol/L; <80 g/L; transfusion indicated	Life-threatening consequences; urgent intervention indicated	Clinical signs and symptoms are not taken into consideration for grading.
Leukocytosis	-	-	>100,000/mm ³ ; >100 x 10 ⁹ /L	Clinical manifestations of leucostasis; urgent intervention indicated	Clinical signs and symptoms are not taken into consideration for grading; Added ranges in SI unit (x 10 ⁹ /L)
Investigations					
Activated partial thromboplastin time prolonged	>ULN - 1.5 x ULN	>1.5 - 2.5 x ULN	>2.5 x ULN; bleeding	-	Clinical signs and symptoms are not taken into consideration for grading.
Alanine aminotransferase increased	>ULN - 3.0 x ULN if baseline was normal; 1.5 - 3.0 x baseline if baseline was abnormal	>3.0 - 5.0 x ULN if baseline was normal; >3.0 - 5.0 x baseline if baseline was abnormal	>5.0 - 20.0 x ULN if baseline was normal; >5.0 - 20.0 x baseline if baseline was abnormal	>20.0 x ULN if baseline was normal; >20.0 x baseline if baseline was abnormal	Ranges defined for “abnormal baseline” are applied only if baseline > ULN. If baseline < LLN, then ranges for “normal baseline” are applied.

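### Laboratory grade and xULN tables count unchanged baseline abnormalities, no laboratory shift table is planned, and respiratory rate lacks a change-from-baseline condition

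*SAP*

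**What the plan says.** **Laboratory grades.** SAP 5.6.3.1 summarizes, by intervention group, "The proportion of participants with post-baseline values by maximum toxicity grade". Participants at Grade 2 or above are listed. No condition refers to the grade before dosing.

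**Liver tests.** The same section summarizes "Participants with maximum post-baseline elevated liver function tests through Week 16" (and through Week 56) in categories from above 1 x ULN to 20 x ULN or more, again with no baseline condition.

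**Other laboratory output.** "Change from baseline through different study periods in both studies as specified in Section 5.6 will be summarized for chemistry, and hematology tests", with box plots. No laboratory shift table is listed.

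**Grading rules (SAP Appendix 11).** Most rows use limits that do not refer to the participant's baseline. Anemia Grade 1, for example, is "Hemoglobin (Hgb) <LLN - 10.0 g/dL". ALT, AST, ALP, GGT and bilirubin differ: if baseline is above ULN, later values are graded as multiples of baseline (for ALT Grade 1, "1.5 - 3.0 x baseline if baseline was abnormal"). Baseline values of these tests are graded on the normal-baseline ranges. Creatinine at Grades 2 and 3 and low fibrinogen also have baseline-relative ranges.

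**Vital signs.** SAP 5.6.3.2 promises "Incidence of treatment-emergent abnormal vital signs during intervention", as defined in Table 6, for participants with a baseline and a later value. Pulse and blood pressure need both a threshold and a change from baseline. Respiratory rate needs only a value above 20 "breaths per minute".

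**The concern.** A table of worst on-treatment grades is read as showing what happened after dosing. Without a baseline condition it shows post-baseline prevalence, so a participant who enters with a mild abnormality and never changes looks the same as one who developed it on drug.

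Entry to the study does not prevent this. Protocol 5.1, criterion 14, admits values that are Grade 1 when outside the local normal range, and it sets no limit on lipids, CPK, potassium or sodium.

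At stake is how readable the categorical safety tables are. This is the first study of the compound in psoriasis, with 40 participants planned per arm. The plan uses baseline elsewhere: Protocol 9.4.5 counts a pre-existing condition as an intervention-emergent AE when it has worsened, and SAP 5.6.3.3 plans a baseline shift table for the C-SSRS. Laboratory grades have neither.

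**Working it through.** The documents state no figure for this point, so there is none to reproduce. The check applies the SAP's rules to example participants and then illustrates the size.

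**1. Who is counted without any change?** Examples assume values outside local normal limits, since Appendix 11 resets values inside those limits to Grade 0.

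- Hemoglobin 10.5 g/dL before and after, with LLN above 10.5: Grade 1, counted.
- Triglycerides 200 mg/dL before and after: Grade 1, counted. Above 300 mg/dL: Grade 2 or higher, counted.
- Potassium between 3.0 mmol/L and LLN before and after: Grade 2, because Appendix 11 does not assign Grade 1 here. Counted and listed.
- ALT 1.8 x ULN before and after: 1.8/1.8 = 1.0 x baseline, below 1.5, so Grade 0 and not counted in the grade table. It is counted as above 1 x ULN.
- Respiratory rate 22 before and after: meets the Table 6 criterion.

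**2. Which grades are exposed?** Criterion 14 requires hemoglobin at least 10 g/dL, WBC at least 3.5, neutrophils at least 1.5, platelets at least 100, and AST, ALT and ALP at most 2 x ULN. In Appendix 11, Grade 2 begins below 10.0 g/dL, 3.0, 1.5 and 75, and above 3.0 x ULN (AST, ALT) or 2.5 x ULN (ALP). For these tests Grade 2 or higher is excluded at screening, so carry-over is mainly Grade 1, or above 1 x ULN in the liver table. Lipids, CPK, potassium and sodium have no such limit and could carry over at Grade 2 or higher.

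**3. Size, on assumed rates.** Let b be the share abnormal at baseline who stay abnormal without worsening, and p the new-onset rate among the rest.

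- Counted as planned: b + (1 − b)p.
- Counted only if worse than baseline, all 40 in the denominator: (1 − b)p.
- Standard error of the difference: √[p₀(1 − p₀)/40 + p₁(1 − p₁)/40], where p₀ and p₁ are the tabulated proportions.

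Assumed p: 5% placebo, 15% active.

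| b | As planned | Ratio | Worsened only | Ratio | Difference (both) | SE, planned / worsened |
|---|---|---|---|---|---|---|
| 5% | 9.75% vs 19.25% | 1.97 | 4.75% vs 14.25% | 3.0 | 9.5 points | 7.8 / 6.5 |
| 10% | 14.5% vs 23.5% | 1.62 | 4.5% vs 13.5% | 3.0 | 9.0 points | 8.7 / 6.3 |
| 20% | 24% vs 32% | 1.33 | 4% vs 12% | 3.0 | 8.0 points | 10.0 / 6.0 |
| 30% | 33.5% vs 40.5% | 1.21 | 3.5% vs 10.5% | 3.0 | 7.0 points | 10.8 / 5.7 |

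At b = 20% the standard error as planned is √(0.24 × 0.76/40 + 0.32 × 0.68/40) = √0.0100 = 10.0 points. Counting only worsening it is √(0.04 × 0.96/40 + 0.12 × 0.88/40) = √0.0036 = 6.0 points.

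The expected difference is the same under both counts. The ratio and the precision change. At b = 0 the two counts agree.

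**4. Would one rule, post-baseline grade above baseline grade, work for every test?** No. ALT 1.8 x ULN at baseline is Grade 1 on the normal-baseline ranges. A later 5.3 x ULN is 5.3/1.8 = 2.9 x baseline, still Grade 1. The rule would drop this rise from the count, because baseline would be adjusted for twice. In the xULN table it moves from above 1 to at least 5 x ULN and stays visible.

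Likewise, requiring a baseline respiratory rate of 20 or less would drop a rise from 22 to 40.

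**The case against.** A reader might infer that the safety tables will hide any real drug effect. The documents do not support that, for several reasons.

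- Change-from-baseline summaries and box plots by group are planned for chemistry and hematology. Protocol 8.2.4 has clinically relevant laboratory changes recorded as AEs, and the DMC reviews safety data.
- The main liver tests are already graded against an abnormal baseline. For ALT and AST, the categories from 3 x ULN upward and the potential Hy's Law summary will be largely new events, given the 2 x ULN entry limit.
- Tabulating by maximum grade means that a move from Grade 1 to Grade 2 appears in another row.
- The expected risk difference is unaffected. SAP 5.6 plans no formal safety comparison, so no test loses power, and it adds a combined active column (planned 200 versus 40).
- All rates in the table above are assumed, and the model takes every baseline abnormality to persist without worsening.

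A reader might also take Table 6 as an instruction to count baseline cases of high respiratory rate. It is better read as an ambiguity: the sentence above it says treatment-emergent and requires a baseline value, but the term is not defined for vital signs.

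These points limit the concern but do not remove it. Group means do not show which participants newly crossed a threshold, which is what a grade table is for. Respiratory rate is not named among the vital signs with change-from-baseline summaries, so that route is not clearly available for it.

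**Conclusion.** The point holds as a minor weakness of descriptive tables. SAP 5.6.3.1 ignores baseline status in the grade and xULN tables and plans no laboratory shift table, so unchanged abnormalities are counted for tests not graded against baseline and for the category above 1 x ULN. The carry-over is mainly Grade 1 where criterion 14 sets limits, and possibly Grade 2 or higher where it does not.

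On the assumed rates (5% versus 15% new onset, 5% to 30% abnormal at baseline), a ratio of 3.0 would appear as 1.97 down to 1.21, with the risk difference unchanged and its standard error larger. The real size depends on a baseline prevalence that the documents do not give. If it is near zero, the effect is negligible.

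The respiratory-rate row is inconsistent with the other rows of Table 6 and with the name of the output, and needs a stated rule.

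**What to change.** 1. In SAP 5.6.3.1, add shift tables of baseline against worst post-baseline value, one for CTCAE grade and one for xULN category.
2. For tests that Appendix 11 grades without reference to baseline, also report participants whose maximum post-baseline grade exceeds their baseline grade. Do not apply this rule to ALT, AST, ALP, GGT, bilirubin or other rows already graded relative to baseline. Show the liver tests by xULN shift instead.
3. In Table 6, count a respiratory rate above 20 only with an increase from baseline, in the same form as the pulse and blood-pressure rows, so that worsening from an already high value still counts. The sponsor would need to set the increment, because the documents give none.

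The cost is some SAP wording, a little programming and one or two more tables. Baseline is defined in SAP 5.1, Appendix 11 already says how to grade it, and the data are already collected.
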